## 2. TRIAL DESIGN, OBJECTIVES AND HYPOTHESES

#### 2.1 Overview

#### 2.1.1 Design

This is an investigator-initiated, randomized, parallel-grouped, double-blinded, superiority trial, investigating the combination of IV LDK and IV morphine versus IV morphine and placebo as regards to analgesic effect.

## 2.1.2 Hypotheses

- The combination of IV LDK and IV morphine will be superior to IV morphine alone as regards analgesic effect measured as reduction on the NRS scale.
- The combination of IV LDK and IV morphine will provide a larger reduction on the NRS scale for patients with a prior use of opioids than for patients with no prior use of opioids.
- The combination of IV LDK and IV morphine will reduce the opioid consumption within the first hour.
- The frequency of side effects will be similar in the two treatment groups (ketamine vs. placebo)

\*\* After longer use (> 3 days).

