## Statistical analysis plan for KetMo, NCT 05422001

Aarhus. September 15th 2023

The following plan for data analysis was decided upon at a meeting with all members of the steering committee on September 15th, 2023. The plan was made before A and B lists were obtained from the hospital pharmacy.

This study will be undertaken as an equivalence trial with the application of intention to treat analysis.

Missing data are assumed to be missing at random, no imputations.

In brief:

A study enrollment flow diagram in accordance with the CONSORT (Consolidated Standards of Reporting Trials) will be prepared. Patient characteristics and outcome measures will be reported as means, standard deviations (SDs), medians, interquartile ranges (IQRs), and percentages, as appropriate.

Primary outcome will be comparing average change of NRS at 10 minutes between the intervention and control group and analyzed using appropriate test depending on distribution. Primary outcome includes initial analysis of all included patients (n=116) and sub-analysis in two groups (prior opioid use / no prior opioid use). Appropriate test according to potential difference in NRS at T0 in the two groups (prior opioid use) will be applied for comparing the differences in NRS between the two groups.

NRS will be reported as median (interquartile range) and compared between groups at the various times using the Mann–Whitney U test. If normal distributed a multilevel mixed effects linear regression will be carried out.

Categorical data (number of patients with Ramsay Sedation Scale Level 2, any adverse events during observation) are reported as numbers (%) with 95% confidence intervals and compared using the  $\chi^2$  test. Analysis of other secondary outcomes will be dichotomized and presented for relevant time points,  $\chi^2$  test.

Secondary outcome concerning Rescue opioid will be evaluated as time to event (opioid) – non parametric – Kaplan Meier estimate will be considered, if appropriate. Alternative rescue opioid yes/no – binary regression if assumptions are fulfilled.

All P-values will be two-sided, and those below 0.05 considered significant.

Detailed statistical plan are written, printed, signed and stored in Trial Master File

[name]

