#### 5. SAMPLE SIZE CALCULATION AND STATISTICAL ANALYSIS PLAN

## 5.1 Sample size calculation

We consider a mean reduction in pain intensity of 1 (SD  $\pm$ 2) on the NRS scale to be realistic in the control group and that the reduction should be 2.5 (SD  $\pm$  2) in the intervention group for the addition of LDK to be meaningful. Based on these estimates, an alpha of 5%, a power of 90% and a two-sample t-test (assuming that the pain reduction is normally distributed), a sample size of 78 patients is required; 39 in each treatment arm (two independent samples =156 patients).

The primary (continuous) and secondary outcomes (binary and continuous variables) will be presented as follows: Categorical variables will be compared using Fisher's exact test and continuous variables

using t-tests or Wilcoxon rank-sum test as appropriate. P < 0.05 will be considered statistically significant.

To investigate the hypothesis of heterogeneity in effect of LDK addition depending on prior morphine use, we will compare treatment effect between the two groups (no prior morphine use vs prior morphine use). If we assume the two groups to have equal size (78 patients) then the expected SE of the difference between treatment effects of the two groups (no prior morphine vs prior) will be 0.64, i.e. the corresponding 95% confidence interval will have a width of approximately 2.6.

To handle potential differences in baseline pain intensity between the standard and the LDK treatment group, we will assess the relative (%) change in NRS from baseline (T0) to 10 min after administration of study medicine in a supplemental post-hoc analysis. The relative change in pain scores will be assessed by multilevel mixed effect ordinal logistic regression model.

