**RASS** 

Need for rescue morphine and total use of morphine

Physician reported side effects: nystagmus, hypertension, respiratory depression, bradycardia, arrhythmia.

TOKS and triage values as standard procedures

Patient-reported side effects: nausea, lightheadedness or dizziness, dry mouth, disorientation, euphoria, itching, tinnitus, double vision, abnormal dreaming or hallucinations.

Patient satisfaction. To be able to compare with other and future studies "no pain" and "worst pain imaginable" are chosen as anchors.

Provider satisfaction with pain control will be recorded on the 4-point Likert scale with 0 being "completely unsatisfied" and 3 being "very satisfied.

Protocol violation.

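### The hypothesis that side effects are similar is backed only by tests of difference, with no margin and no confidence interval planned for the between-arm difference

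*Combined protocol and SAP*

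**What the plan says.** Protocol section 2.1.2 lists four hypotheses. The fourth is that "The frequency of side effects will be similar in the two treatment groups (ketamine vs. placebo". Safety is part of the objective (section 2.1.5), and side effects are a secondary outcome (section 4.2.1).

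The SAP states that categorical data, including "any adverse events during observation) are reported as numbers (%) with 95% confidence intervals and compared using the" chi-square test. For the remaining secondary outcomes it adds: "Analysis of other secondary outcomes will be dichotomized and presented for relevant time points", again with chi-square. Its decision level is "All P-values will be two-sided, and those below 0.05 considered significant". Protocol section 5.1 names a different test: "Categorical variables will be compared using Fisher's exact test and continuous variables" by t-test or rank-sum test.

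The SAP also says "This study will be undertaken as an equivalence trial with the application of intention to treat analysis", while protocol section 2.1.1 describes a superiority trial. Neither document sets an equivalence margin for any endpoint. Neither gives an expected side-effect rate at the study dose, or a criterion for calling the arms similar.

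The solicited effects are listed twice. Section 6.2.2 has the physician record "nystagmus, hypertension, respiratory depression, bradycardia, arrhythmia". Section 2.5.1 has hallucinations in place of arrhythmia. Dry mouth is a patient-reported item only in section 6.2.2.

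**The concern.** A test of difference can contradict a claim of similarity but cannot support one. A P value of 0.05 or more may mean that the arms are alike, or that the trial is too small to separate them. Telling these apart takes an interval for the between-arm difference, and a claim of similarity also takes a limit to hold that interval against. The plan has neither.

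At stake is the safety statement in the main publication. The trial was sized for a pain difference, so its precision on side effects is whatever that sample happens to give. Without an interval for the difference, a reader cannot see how large an excess on ketamine remains compatible with the data.

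**Working it through.** **What the trial was sized for.** Section 5.1 uses reductions of 1 and 2.5 on the NRS, SD 2, alpha 5% and power 90%. The normal approximation gives n = 2 × 2² × (1.960 + 1.282)² / 1.5² = 37.4, so 38 per arm. The two-sample t-test gives 38.35, so 39 per arm, which reproduces the stated figure (78 per opioid-use group, 156 in total). No corresponding calculation exists for side effects.

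**Inputs for side effects.**
- Arm sizes: 80 per arm from the protocol's 160 at 1:1 (section 2.2), and 58 per arm from the SAP's 116. The even split of 116 is an assumption.
- Event rates: assumed, 5% to 50%. Section 1.2.5 gives frequencies for anesthetic doses only. Section 1.2.4 says psychoperceptual effects are few or absent at the study dose but gives no rate.

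**Precision of the risk difference.** With equal true rates p, the 95% half-width is 1.96 × √(2p(1 − p)/n). For p = 0.20 and n = 58 this is 1.96 × √(0.32/58) = 0.146.

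| Rate in both arms | 58 per arm | 80 per arm |
|---|---|---|
| 5% | ±7.9 points | ±6.8 points |
| 10% | ±10.9 | ±9.3 |
| 20% | ±14.6 | ±12.4 |
| 30% | ±16.7 | ±14.2 |
| 50% | ±18.2 | ±15.5 |

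**How often a real excess gives P ≥ 0.05.** The exact power is the sum, over all pairs of counts (x, y), of Bin(x; n, p₁) × Bin(y; n, p₂) for the pairs where the test gives P < 0.05. The chance of a non-significant result is one minus this sum.

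| Placebo vs ketamine | Chi-square, 58 | Chi-square, 80 | Fisher, 58 | Fisher, 80 |
|---|---|---|---|---|
| 20% vs 35% | 55% | 42% | 63% | 50% |
| 20% vs 30% | 76% | 69% | 82% | 75% |
| 10% vs 20% | 67% | 58% | 76% | 65% |

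For 20% vs 35%, for example, chi-square power is 0.447 at 58 per arm and 0.576 at 80.

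**One possible result.** Suppose 27/58 on ketamine and 17/58 on placebo (47% vs 29%). Chi-square = 116 × (27 × 41 − 17 × 31)² / (58 × 58 × 44 × 72) = 3.66, P = 0.056. The difference is 17.2 points, with a 95% interval (Newcombe) from −0.4 to +33.4 points. It is not significant, yet it plainly does not show similarity.

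**What a claim of similarity would need.** Suppose the true rates are equal, the whole 95% interval must lie within ±m, and power is 80%. Then n per arm = 2p(1 − p)(1.960 + 1.282)²/m². At a 20% rate this is 337 for m = 10 points, 150 for 15 and 85 for 20. At a 5% rate it is 100 for 10 points and 45 for 15. These margins are illustrative only.

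**The case against.** A reader might infer that the sponsor means to declare side effects similar whenever P is 0.05 or more. No sentence in either document says so. Section 2.1.2 states an expectation, and the SAP describes a way of reporting plus a test. The percentages above are therefore chances of a non-significant result, not of a planned false conclusion.

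The plan is also not bare of intervals. The SAP promises 95% confidence intervals for categorical data, and protocol section 5.2 fixes 95% coverage throughout. The public SAP calls itself brief and refers to a detailed plan in the Trial Master File, which is not among these documents and may contain a criterion. Rates may be low at this dose. At 5% and 80 per arm the half-width is 6.8 points, which could exclude a fairly modest excess. Side effects are secondary, and the sample was never meant to settle them.

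All of this stands as a limit on the point, but it does not remove it. The intervals described attach to numbers and percentages rather than to the difference. The public plan has no criterion for similarity, and both named tests are tests of difference.

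A reader might also infer that the two lists leave the safety endpoint undefined. That goes too far. The SAP endpoint is any adverse event during observation, section 2.5.1 invites spontaneous reports, and hallucinations are on the patient-reported list in both sections. Section 6.2.1 describes the variable list as an overview, with details in the data dictionary.

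**Conclusion.** The planned analysis cannot support the fourth hypothesis as worded. That follows from the type of test and holds for chi-square and Fisher's test alike, at 116 or 160 patients. How wide the uncertainty is depends on assumed rates of 5% to 50% and, for 116, on an assumed even split. The documents do not define a clinically important excess, so they do not support saying that the trial can never exclude one; for rare effects it may exclude a modest excess. The primary endpoint is not affected. The choice between two tests and the differing lists are minor consistency points.

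**What to change.** In the SAP, report the risk difference (ketamine minus placebo) with its 95% confidence interval for any adverse event during observation and for each solicited effect. Interpret safety by the excess that the upper limit does not exclude, and state that P of 0.05 or more will not be taken as evidence of similarity.

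Reword the fourth hypothesis as a descriptive estimate. If similarity is to be claimed, justify a margin before unblinding, preferably before the data are split into groups A and B, and claim it only if the interval lies within that margin. An upper limit with no threshold describes uncertainty but cannot establish similarity. If no margin is set before unblinding, use the descriptive version.

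As minor edits, reconcile the solicited lists in sections 2.5.1 and 6.2.2 and name one test for categorical data.

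The cost is a few sentences and one added interval per outcome, from data already collected and with no extra patients. The downside is a more modest safety claim.

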#### 2.1.3 Location

The study will be conducted at Aarhus University Hospital

## 2.1.4 Participants

160 patients presenting in the ED with NRS ≥ 5 will be enrolled.

## 2.1.5 Objective

To determine efficacy and safety of IV LDK as an adjunct to IV morphine for the treatment of severe acute pain in the ED and compare the effect in patients with a prior use of opioid and patients without.

#### 2.2 ALLOCATION

Patients fulfilling all inclusion criteria and no exclusion criteria will be randomized as follows:

Group 1 = patients with a prior use of opioids.

Group 2 = patients without a prior use of opioids.

Patients in group 1 are allocated randomization numbers 101-190

Patients in group 2 are allocated randomization numbers 201-290

There are 10 additional numbers in each group to be used if a patient is excluded after the administration of study medicine.

If a patient is excluded after randomization, but before study medicine is administered, the randomization number can be re-used by adding and registering a, b, c and so on.

Patients (n=160) will be randomized in a 1:1 ratio to either s-ketamine or placebo (NaCl) in blocks of 2, 4 and 6 patients

The randomization process will be performed by the hospital pharmacy using www.sealedenvelope.com.

The randomization list is kept at the hospital pharmacy during the study and only delivered to the PI when the inclusion and the data analysis are completed.

PI will be provided with numbered blinded kits including either S-ketamine or placebo ensuring allocation concealment.

## The kit consist of:

#### Active:

Esketamin "Orifarm" 5 mg/ml
 NatriumChloride Fresenius Kabi 20 x 10 ml
 Emballage, 1 ml, neutral syringes
 Emballage, cardboard (with label)
 Labels, 2 pieces, for the syringes
 Envelope for emergency unblinding

## Placebo:

NatriumChloride Fresenius Kabi 20 x 10 ml 1 x 10 ml
 Emballage, 1 ml, neutral syringes 2 pieces
 Emballage, cardboard (with label) 1 karton
 Labels, 2 pieces, for the syringes 2 pieces
 Envelope for emergency unblinding

## 2.3 INTERVENTIONS

## 2.3.1 Intervention groups

	Morphine + LDK	Morphine + Placebo
Prior opioid use	N 40 IV morphine (15 % of the total 24-hour opioid consumption)	N 40 IV morphine (15 % of the total 24-hour opioid consumption)
No prior opioid use	Ketamine 0,1 mg/kg  N 40  IV morphine, 0.05- 0.1 mg/kg  +  Ketamine 0,1 mg/kg	Placebo (saline)  N 40  IV morphine, 0.05- 0.1 mg/kg  + placebo (saline)

#### 2.3.2 Concomitant interventions

All procedures, except for the administration of study medicine and data collection for the study purpose, will be conducted according to the standard at Aarhus University Hospital.

During the observational period, 120 min, relevant procedures will be registered in eCRF:

- Nerve block
- Repositioning of joints/fractures or casting
- Paracetamol and NSAID

2.3.3 Criteria for modification of interventions for a given trial participant and protocol violations

The clinical team may at any time violate the protocol if they find it to be in the interest of the

participating patient.

#### 2.3.4 Assessment of participant compliance

The trial site is monitored through the electronic case report form (eCRF). In addition, the trial will be monitored according to the Good Clinical Practice (GCP) directive and the monitoring plan.

## 2.4 BLINDING

The trial intervention (morphine + LDK vs. morphine + placebo) will be blinded for investigators, clinical staff, and participants.

Only the pharmacy providing the numbered kits and the nurse who draw the medication will be aware of the allocation.

Patients will be randomized according to the allocation list.

The randomization number will be entered directly in the eCRF.

[figure not shown]
Study medicine is delivered by the pharmacy in blinded kits, the PI provides a study nurse (who is not otherwise involved in the study) with the kit and he or she will draw the study medicine in the two, 1 ml, syringes contained in the kit, mark them with the labels in the kit and hand them over to the PI.

Both ketamine and NaCl is colorless and without any identifying features.

The PI has entered the sex and weigth in the eCPR and a calculated field gives the ideal weigth. The PI administers the correct doses according to ideal weigth.

Doses are marked in table 1, (ideal weight, 0.1 mg/kg).

## Labels (Danish):

In the blinded intervention kit, a sealed opaque envelope will contain the allocation assignment which will allow for emergency unblinding. The decision to unblind will be at the complete discretion of the treating physician and clinical team. However, we do not expect scenarios where emergency unblinding will be necessary. In case unblinding occurs, the reason(s) will be clearly documented in the case report form. The patient will remain in the trial.

Table 1

Ideal weight*, kg	40	45	50	55	60	65	70	75	80	85	90	95	100	105	110
Ketamine, mg	4	4,5	5	5,5	6	6,5	7	7,5	8	8,5	9	9,5	10	10,5	11
Study medication, ml (S-ketamine 5 mg/ml or placebo)	0,8	0,9	1	1,1	1,2	1,3	1,4	1,5	1,6	1,7	1,8	1,9	2	2,1	2,2

\*ideal weight: height (in cm) - 100

If cancellation/postponement of treatment or withdrawal of consent occurs before the study medication is given, but after randomization has taken place, the randomization number will not be reused. Besides study medication, emergency department staff provides usual pain treatment (0.05-0.1 mg/kg morphine or if the patient has a prior use of opioids 15% of 24 hour dose in morphine equivalent – in both cases titration until NRS  $\leq$  3.)

The unblinded pharmaceutical staff and nurse who draws study medicine will not be involved in outcome evaluation or patient treatment.

## 2.5 TRIAL PROCEDURES

## 2.5.1 Patients

The trial procedures will be limited to the interventions given with the first dose of morphine (see section 2.3)

Data will be obtained from the study specific eCRF and from the electronic medical records.

 $T_0$  defined as when the ED physician/nurse evaluates NRS and the PI gives the study medication.

The trial and observation period is  $T_0$  - 120 min.

	T 0	10 min	20 min	30 min	45 min	60 min	120 min
NRS	Х	х	Х	Х	Х	Х	х

Patient rated		Х					Х
pain relief*							
Vital	Χ	Х	Х	Χ	Х	Χ	Х
parameters							
Patient		х		Х			х
reported side							
effects**							
Physician							х
reported side							
effects***							
Provider							x
satisfaction							
score****							
Patient							x
satisfaction							
score							
RASS****	 	Х	Х	Х	Х	Х	Х

\*Patients will be asked to rate their pain relief on a 6-point scale ("worse pain," "no," "little," "moderate," "good," or "complete pain relief").

In addition, patients are encouraged to spontaneously report any other side effects/adverse advent. The timing of onset and resolution of all adverse effects during the observation period will be recorded.

- \*\*\*Physician-reported side effects: nystagmus, hypertension, respiratory depression, bradycardia, hallucinations.
- \*\*\*\*Provider satisfaction with pain control will be recorded on the 4-point Likert scale with 0 being "completely unsatisfied" and 3 being "very satisfied.
- \*\*\*\*\*Richmond Agitation-Sedation Scale (RASS) will be used to evaluate agitation or sedation. (appendix 2)

TRIAGE and TOKS (tidlig opsporing af kritisk sygdom) according to the standard at AUH will be used to evaluate differences in vital parameters.

\*\*Patient-Reported Side effects: nausea, lightheadedness or dizziness, disorientation, euphoria, itching, tinnitus, double vision, abnormal dreaming or hallucinations.

There will be no questionnaires for the participants to answer, they will be asked verbally and their answers will be entered in RedCap.

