#### 1.2.4 Ketamine

Ketamine's analgesic properties in sub-anesthetic doses (0.1-0.5 mg/kg) have been recognized for decades (average anesthetic induction dose is 2 mg/kg) and S-ketamine produces analgesia at plasma concentrations of 100 to 200 ng/mL, which represent a very small fraction of plasma concentrations after general anesthesia doses (9000–25,000 ng/mL).

The recommended sub-anesthetic dose of ketamine used in pain treatment or in the prehospital emergency setting is 0.125-0.25 mg/kg bolus given IV over at least one minute. In these doses LDK show analgesic effects without sedative or hypnotic effect. When used as per- and postoperative pain treatment at AUH doses are (perioperative) 0.3 mg/kg/h and (postoperatively) 0,02 mg/kg/h.

Studies from the ED  $^{46,59,60,61,62}$  finds little to no psychoperceptual effects at the dose of 0.1 mg/kg as will be used in this study.

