#### 3.3 Exclusion criteria

- 1) Initial management by trauma-team
- Systolic blood pressure ≥ 180 mmHg, severe untreated arrhythmia, unstable angina pectoris, recent myocardial infarction ( < 30 days), severe heart failure (Ejection fraction < 40 %)

- 3) Symptoms of untreated hyperthyroidism
- 4) Cirrhosis with ascites
- 5) Known/suspected pregnancy, or breastfeeding
- 6) Patients, for whom consent is not obtainable or psychiatric forced treatment.
- 7) Previously enrolled in the trial
- 8) Psychiatric illness prior to admission defined as prior psychosis/schizophrenia
- 9) Diagnosed untreated glaucoma
- 10) Known hypersensitivity to ketamine or to any excipient or prior use of ketamine with a negative experience (i.e. hallucinations)
- 11) Patient clearly influenced by drugs or alcohol

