**Exclusion criteria** 

Opioids given before study medication (i.e. in ambulance)

Date and time consent for data collection is obtained

Patient demographics and characteristics

Unique patient identifier (CPR number)

Age

Sex

Height

Weight Medications prior to enrollment Prior opioid use, dose, duration Reason for prior opioid use (cancer/non-cancer pain, postoperative, addiction) Cancer/non-cancer Site of pain/injury: Fracture/orthopedic Abdominal/flank Groin pain Postoperative pain Other/unknown Prior to randomization: Vital parameters NRS At 10, 20, 30, 45 60 and 120 min after randomization: NRS

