6.6 Data obtained from patient records

6.6.1 Data that will be obtained before informed consent and inclusion

The electronic patient record will only be screened for in- and exclusion criteria (see page 22-23), pain intensity and opioids given before the informed consent, i.e in ambulance. If a patient is excluded the reason for exclusion will be entered in the screening log.

No other data will be obtained.

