6.6.2 Data that will be obtained after informed consent and inclusion

Reason for contact to the ED (ie abdominal pain, broken ankle)
Use of opioids prior to the admission (yes or no, drug and dose)
Use of other analgesic except NSAIDs and paracetamol

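### Analgesia given before study drug is not clearly defined in the protocol and not used in the analysis, so it can dilute and add noise to the LDK-versus-placebo contrast

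*Combined protocol and SAP*

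**What the plan says.** **Timing of study drug.** Section 2.5.1 of the protocol reads: "The trial procedures will be limited to the interventions given with the first dose of morphine". It refers to section 2.3, which does not say whether this is the first dose in the ED or the first in the episode. T0 is the moment when ED staff score pain and study medication is given.

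**Earlier opioid.** The variable list in section 6.2.2 contains "Opioids given before study medication (i.e. in ambulance". In the extracted text this item follows the words for exclusion criteria, but those words are themselves an entry in the list of recorded variables. Section 6.6.1 supports that reading: in addition to the inclusion and exclusion criteria, the record is screened before consent for "pain intensity and opioids given before the informed consent, i.e in ambulance".

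**Earlier ketamine.** Section 1.2.4 gives a ketamine dose "used in pain treatment or in the prehospital emergency setting", citing the same esketamine product that is in the active kit (section 2.2). In section 3.3 the only ketamine criterion is hypersensitivity or "prior use of ketamine with a negative experience (i.e. hallucinations". The nearest other criterion is "Patient clearly influenced by drugs or alcohol".

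**Other fields.** Section 6.2.2 also lists medicines taken before enrolment, and section 6.6.2 lists "Use of other analgesic except NSAIDs and paracetamol".

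**Analysis.** Protocol sections 5.1 and 5.2 and the SAP compare the 10-minute NRS change between arms, overall and by prior opioid use. Section 3.2 defines prior use as daily use in the week before admission. No analysis refers to analgesia given before T0.

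**The concern.** The trial asks what a single low dose of ketamine adds to morphine at 10 minutes. That question is clean only if control patients are free of ketamine and other recent analgesia is either absent or accounted for.

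As written, a patient already given ketamine in this episode without a bad reaction can be enrolled and counted as a placebo control, or can receive study ketamine on top of it. Either way, that patient tells us less about ketamine versus none.

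Opioid given shortly before T0 may still be acting in the 10-minute window and may also lower the later need for morphine, a secondary outcome. The stratification does not capture it: a patient whose only opioid was in the ambulance belongs to the stratum without prior use. A baseline influence on the primary outcome is therefore recorded but left unused.

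**Working it through.** **1. The texts side by side.** Section 2.5.1 ties study drug to a first morphine dose. Sections 6.2.2 and 6.6.1 provide for opioid before that dose. The three agree only if first means first in the ED, which the text does not state. Section 1.2.4 describes ketamine before hospital, and section 3.3 has no criterion for ketamine in the current episode. Criterion 11 need not catch such a patient, because section 1.2.4 says that the doses it cites relieve pain without sedation.

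**2. The plan's own sample size.** Inputs from sections 5.1 and 5.2: mean reductions 1 and 2.5 (difference 1.5), SD 2, two-sided alpha 5%, power 90%, two-sample t-test.

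- Normal approximation: n per arm = 2 × (1.960 + 1.282)² × 2² / 1.5² = 37.4, so 38.
- Noncentral t: 38 per arm gives power 0.897 and 39 gives 0.905. The stated 39 per arm (78 per stratum, 156 in all) is reproduced.

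**3. Illustration for ketamine before T0.** Assume that a share f of each arm is pre-treated, that study drug keeps a fraction r of its effect in them, and that the SD stays at 2. Then

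expected difference = 1.5 × [1 − f(1 − r)].

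The pessimistic case is r = 0, giving 1.5 × (1 − f). Power comes from the noncentral t with 2n − 2 degrees of freedom and noncentrality difference / (2 × √(2/n)). For n = 39 the noncentrality is 1.5/0.453 = 3.31 with no pre-treatment and 1.35/0.453 = 2.98 at f = 0.10. The SAP's 116 patients are taken as 58 per arm.

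| f (r = 0) | Difference | Power, 39 per arm (one stratum) | Power, 58 per arm (SAP n=116) | Power, 78 per arm (both strata) | n per arm for 90% |
|---|---|---|---|---|---|
| 0 | 1.50 | 0.905 | 0.980 | 0.996 | 39 |
| 0.05 | 1.425 | 0.874 | 0.967 | 0.993 | 43 |
| 0.10 | 1.35 | 0.837 | 0.950 | 0.987 | 48 |
| 0.20 | 1.20 | 0.744 | 0.893 | 0.961 | 60 |
| 0.30 | 1.05 | 0.629 | 0.800 | 0.903 | 78 |

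If study drug keeps half its effect (r = 0.5), f = 0.10 gives 1.5 × 0.95 = 1.425, which is the 5% row. Every f and r here is an assumption; the documents supply neither.

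**4. Opioid before T0.** If a share q had it and their mean 10-minute change differs by d, it adds q(1 − q)d² to the variance within each arm. The documents give neither q nor d, so no figure is offered. The planning SD of 2 may already include some of this spread.

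**The case against.** Several points on the other side stand.

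- **First dose.** The natural reading is the first ED dose given with study drug: T0 is set in the ED and ED staff give the morphine. The sentence limits trial procedures to one occasion; it is not an eligibility rule. The trial flowchart, which might show the sequence, is not in the text available. A reader might infer that patients with ambulance opioid are enrolled in breach of the protocol. The documents do not support that; the wording needs clarifying.
- **Ketamine before arrival is hypothetical.** Section 1.2.4 gives a recommended dose and does not say that local ambulances use the drug. Where the protocol describes treatment before arrival it names only opioids. Patients must still have NRS of at least 5, and trauma-team patients are excluded.
- **Bias.** A reader might infer that contaminated controls tilt the result. Pre-treatment can occur in either arm, and allocation is randomised and blinded, so it is balanced in expectation.
- **Total dose.** A reader might add the cited 0.125–0.25 mg/kg to the trial's 0.1 mg/kg, get 0.225–0.35 mg/kg, and infer a safety problem. Section 1.2.4 itself describes 0.1–0.5 mg/kg as sub-anesthetic, so the sum does not support that inference.
- **Washout.** None is stated, but broad entry is a declared aim (section 3.2) and section 8.1 requires prompt treatment. Its absence is not a flaw shown by the documents.
- **Unseen plan.** The SAP refers to a detailed plan in the Trial Master File. The missing analysis is established only for the public text.

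None of this removes two facts: the eligibility text leaves ketamine in the current episode open, and the public analysis text ignores a recorded baseline influence on the primary outcome.

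**Conclusion.** The point holds as a modest, inexpensive improvement. The protocol does not define first dose, does not say whether ketamine earlier in the episode is compatible with entry, and plans no use of analgesia data from before T0. The expected harm is dilution and noise, not bias.

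Its size cannot be derived from the documents. Under the pessimistic assumption of no added effect in pre-treated patients, a 10% share would cost 0.15 points of the planned difference (1.50 to 1.35) and about 7 percentage points of power within a stratum (0.905 to 0.837). At n=116 the pooled comparison would keep power of 0.950. If no enrolled patient had ketamine beforehand, this part has no numerical effect and only the opioid covariate and the wording remain.

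**What to change.** 1. **Wording.** Reconcile sections 2.5.1, 6.2.2 and 6.6.1 by stating whether the first dose means the first ED dose given together with study drug.
2. **Eligibility text.** Reconcile sections 1.2.4 and 3.3. The sponsor should state whether patients given ketamine in the current episode are eligible, bearing in mind that they cannot serve as ketamine-free controls. That decision is clinical and is left to the sponsor. The SAP already counts 116 included patients; if enrolment has closed, this step serves to describe who was admitted.
3. **Analysis.** Before the A and B lists are opened, pre-specify:
   - the 10-minute NRS comparison adjusted for opioid before T0 (yes/no, already in the eCRF), for example in a linear model beside the planned test;
   - a sensitivity analysis that leaves out, from both arms, patients with ketamine recorded before T0 in the existing fields (sections 6.2.2 and 6.6.2). Because this exposure precedes T0, study drug cannot have influenced who is left out.
   
   First check in the data dictionary that those fields identify ketamine and its timing, since the dedicated field names only opioids. If the lists have already been opened, label both analyses post hoc.

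The cost is one reworded sentence, one eligibility clarification and a small amount of extra analysis on fields already listed for collection. If enrolment is still open, a few fewer patients may be eligible, depending on the sponsor's decision.
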